## 12. Dummy Table List

Analysis Criteria/ Analysis Set	Table No.	Analysis Variables	Group Variables	Note
Disposition of Subjects	0101	Disposition of Subjects	ALL	
	0102	Detailed reports on discontinued subjects	ALL	
	0103	Analysis Set	ALL	
Demographics FAS	0201	Gender	V1(Screening)	Medifoam vs. Betafoam
	0201	Age(Years)	V1(Screening)	Medifoam vs. Betafoam
	0201	Age(20-29, 30-39, 40-49, 50-59, 60-69, 70 or more)	V1(Screening)	Medifoam vs. Betafoam
	0201	Body Weight	V1(Screening)	Medifoam vs. Betafoam
	0201	Height	V1(Screening)	Medifoam vs. Betafoam
	0201	Breast Feeding(Female Only)	V1(Screening)	Medifoam vs. Betafoam
	0201	Possibility of Pregnancy(Female Only)	V1(Screening)	Medifoam vs. Betafoam
	0201	Reason for not being able to pregnant	V1(Screening)	
	0201	Countermeasure for pregnancy	V1(Screening)	
	0201	Alcohol consumption	V1(Screening)	Medifoam vs. Betafoam
	0201	Nicotine consumption	V1(Screening)	Medifoam vs. Betafoam
	0201	Urine HCG test results	V1(Screening)	Medifoam vs. Betafoam
	Medical History FAS	0301	Pressure Ulcer	V1(Screening)
0302		Hypersensitivity	V1(Screening)	Medifoam vs. Betafoam
0303		Other Medical History(Past/Current)	V1(Screening)	Medifoam vs. Betafoam
0304		Past Medical History (SOC/PT)	V1(Screening)	Medifoam vs. Betafoam
0305		Current Medical History (SOC/PT)	V1(Screening)	Medifoam vs. Betafoam
0306		Surgical Procedure	V1(Screening)	Medifoam vs. Betafoam
0307		List of Surgical Procedure and Indications for subjects who had surgical procedure	V1(Screening)	Medifoam vs. Betafoam
Medication History FAS	0401	Prior/Concomitant Medication(Y/N)	ALL	Medifoam vs. Betafoam
	0402	Prior Medication in detail ((Level 1 / Level 3) of WHO ATC)	ALL	Medifoam vs. Betafoam

Analysis Criteria/ Analysis Set	Table No.	Analysis Variables	Group Variables	Note
	0403	Concomitant Medication in detail ((Level 1 / Level 3) of WHO ATC)	ALL	Medifoam vs. Betafoam
Pressure ulcer assessment at Screening(Visit1) FAS	0501	List of Body Parts where Pressure Ulcer occurred	V1(Screening)	Medifoam vs. Betafoam
	0502	Pressure ulcer size at Screening	V1(Screening)	Medifoam vs. Betafoam
Analysis of endpoints of main interest FAS	0601	Number of patients with complete healing of ulcer within 12 weeks	ALL	Medifoam vs. Betafoam
	0602	Time taken for subjects to reach complete healing of ulcer within 12 weeks	ALL	Medifoam vs. Betafoam
	Figure 0601	Time to complete healing of ulcer within 12 weeks	ALL	Medifoam vs. Betafoam, Kaplan-Meire Plot
	0603	Pressure ulcer size by each time point and change from 1d (Baseline)	ALL	Medifoam vs. Betafoam
	0604	Pressure ulcer size reduction rate based on scale at each time point	ALL	Medifoam vs. Betafoam
	0605	Sub-analysis on Pressure ulcer size reduction rate based on scale at each time point by use of topical antibiotics	ALL	Medifoam vs. Betafoam,
	0606	Sub-analysis on Pressure ulcer size reduction rate based on scale at each time point by use of glucocorticoids	ALL	Medifoam vs. Betafoam
Analysis of other endpoints FAS	0701	PUSH reduction rate at each time point	ALL	Medifoam vs. Betafoam
	0702	Dressing change frequency during the entire study period for subjects on Medifoam	ALL	Medifoam vs. Betafoam
	0703	Dressing change frequency during the entire study period for subjects on Betafoam	ALL	Medifoam vs. Betafoam
	0704	Number of subjects with early completion due to complete healing during the study	ALL	Medifoam vs. Betafoam
	0705	Number of subjects by CSSC signs and symptoms per each visit for subjects on Medifoam	ALL	Medifoam vs. Betafoam
	0706	Number of subjects by CSSC signs and symptoms at each visit for subjects on Betafoam	ALL	Medifoam vs. Betafoam
	0707	Incidence of new infections at the pressure ulcer until Week 12 based on the CSSC	ALL	
Physical Examination Safety	0801~0813	Normal(or Abnormal(NCS))/Abnormal(CS)) cross table for Physical Examination	ALL	Medifoam vs. Betafoam McNemar Test
Vital Sign Safety	0901	Vital Sign Results and Change from Baseline(Temperature)	ALL	Medifoam vs. Betafoam
	0902	Vital Sign Results and Change from Baseline(SBP, DBP, Pulse)	ALL	Medifoam vs. Betafoam
Laboratory Test Safety	1001	Laboratory Test results and Change from Baseline (Hematology)	ALL	Medifoam vs. Betafoam
	1002	Normal(or Abnormal(NCS))/Abnormal(CS)) cross table for Laboratory Test (Hematology)	ALL	Medifoam vs. Betafoam McNemar Test
	1003	Laboratory Test results and Change from Baseline (Blood Chemistry)	ALL	Medifoam vs. Betafoam

Analysis Criteria/ Analysis Set	Table No.	Analysis Variables	Group Variables	Note
	1004	Normal(or Abnormal(NCS)/Abnormal(CS)) cross table for Laboratory Test (Blood Chemistry)	ALL	Medifoam vs. Betafoam McNemar Test
Adverse Events Safety	1101	AE Summary(AE, ADE, SAE, SADE)	ALL	Medifoam vs. Betafoam
	1102~1105	Number and Percentage of subjects with (AE, ADE, SAE, SADE )	ALL	Medifoam vs. Betafoam
	1106~1111	Incidence rate, Number and frequency of (Local AE, ADE, SAE, SADE) by Severity, SAE, Outcome, Relationship with the clinical device, Action taken with the Device, Seriousness	ALL	Medifoam vs. Betafoam
	1112~1117	Incidence rate, Number and frequency of (Other AE, ADE, SAE, SADE) by Severity, SAE, Outcome, Relationship with the clinical device, Action taken with the Device, Seriousness	ALL	Medifoam vs. Betafoam

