15.4 Analysis of safety endpoints

(1) Adverse events

List all adverse events that occurred by group. Record the frequency of adverse events related or unrelated with the investigational device by group. For the number of adverse events and the percentage of subjects who had at least 1 adverse event, present the 95% confidence interval in each

treatment group. Analyze adverse events separately for local adverse events at the target pressure ulcer and other adverse events.

(2) Laboratory test findings

For continuous data, present descriptive statistics (mean, standard deviation, median, minimum, maximum) by group and time point. In addition, tabulate the proportion of normal/abnormal results by time point in each group.

(3) Vital signs

For continuous variables, present descriptive statistics (mean, standard deviation, median, minimum, maximum) for the baseline and end-of-study test findings by group and visit time point.

16. Efficacy assessment methods and criteria, and interpretation methods

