16.2 Assessment criteria and methods

This study is a pilot study with no comparator, so that no formal statistical test will be conducted.

17. Safety assessment methods and criteria, and interpretation methods, including adverse events

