### **(2) Laboratory test findings**

For continuous data, present descriptive statistics (mean, standard deviation, median, minimum, maximum) by group and time point. In addition, tabulate the proportion of normal/abnormal results by time point in each group.

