• More ulcer pain now than in the past	N	N	N	N
Erythema	N	N	N	N
Edema	N	N	N	N
Heat	N	N	N	N
Purulent exudates	N	N	N	N
Sanguinous exudates	N	N	N	N
Serous exudates	N	N	N	N
Delayed healing of the ulcer	N	N	N	N
Discoloration of granulation tissue	N	N	N	N
Friable granulation tissue	N	N	N	N
Pocketing at base of wound	N	N	N	N
Foul odor	N	N	N	N
Wound breakdown	N	N	N	N
Total	N	N	N	N

Table 0706 Number of subjects with CSSC signs and symptoms at each visit for subjects on Betafoam

\*Same as Table 0705

Table 0707 Incidence of new infections at the pressure ulcer until Week 12 based on the CSSC

Treatment group	n (Incidence rate)	95% C.I. of Incidence rate	Frequency	Total
-----------------	--------------------	----------------------------	-----------	-------

Medifoam	x(x.xx%)	(x.xx,x.xx)	xx	xx
Betafoam	x(x.xx%)	(x.xx,x.xx)	xx	xx

8) Physical Examination

Analysis Set: Safety

Table 0801 Normal or Abnormal (NCS)/Abnormal(CS) cross table for Physical Examination (Visit 1 vs. Visit 2)

Visit1(Screening)		Visit2(1d)											
		Medifoam						Betafoam					
		Normal		Abnormal		Total		Normal		Abnormal		Total	
		N	(%)	N	(%)	N	(%)	N	(%)	N	(%)	N	(%)
Variables	Normal	xx	Xx (xx.xx)	xx	xx (xx.xx)	xx	xx (xx.xx)	xx	xx (xx.xx)	xx	xx (xx.xx)	xx	xx (xx.xx)
	Abnormal	xx	Xx (xx.xx)	xx	xx (xx.xx)	xx	xx (xx.xx)	xx	xx (xx.xx)	xx	xx (xx.xx)	xx	xx (xx.xx)
	Total	xx	Xx (xx.xx)	xx	xx (xx.xx)	xx	xx (xx.xx)	xx	xx (xx.xx)	xx	xx (xx.xx)	xx	xx (xx.xx)
P-value		0.xxxx						0.xxxx					
..Rest Variables are omitted in TLF..													

Note) Normal includes normal and NCS, while abnormal refers to CS.

Note) p-value: McNemar test

Table 0702 Normal (or Abnormal (NCS)/Abnormal(CS) cross table for Physical Examination (Visit 1 vs. Visit 3)

\*Same as Table 0801

Table 0803 Normal or Abnormal (NCS)/Abnormal(CS) cross table for Physical Examination (Visit 1 vs. Visit 4)

\*Same as Table 0801

Table 0804 Normal or Abnormal (NCS)/Abnormal(CS) cross table for Physical Examination (Visit 1 vs. Visit 5)

\*Same as Table 0801

Table 0805 Normal or Abnormal (NCS)/Abnormal(CS) cross table for Physical Examination (Visit 1 vs. Visit 6)

\*Same as Table 0801

Table 0806 Normal or Abnormal (NCS)/Abnormal(CS) cross table for Physical Examination (Visit 1 vs. Visit 7)

\*Same as Table 0801

Table 0807 Normal or Abnormal (NCS)/Abnormal(CS) cross table for Physical Examination (Visit 1 vs. Visit 8)

\*Same as Table 0801

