		Min~Max	xx.xx~xx.xx	xx.xx~xx.xx	xx.xx~xx.xx	
	Visit14(85d±2d)	N	xx	xx	xx	0.xxxx*
		Mean±Std	xx.xx±x.xx	xx.xx±x.xx	xx.xx±x.xx	
		Median	xx.xx	xx.xx	xx.xx	
		Min~Max	xx.xx~xx.xx	xx.xx~xx.xx	xx.xx~xx.xx	
	Visit14-Visit1	N	xx	xx	xx	0.xxxx*
		Mean±Std	xx.xx±x.xx	xx.xx±x.xx	xx.xx±x.xx	
		Median	xx.xx	xx.xx	xx.xx	
		Min~Max	xx.xx~xx.xx	xx.xx~xx.xx	xx.xx~xx.xx	
..Rest Variables are omitted in TLF..						

Note) \*: t-test, ¥ : Wilcoxon rank sum test, #: Paired t-test, \$: Wilcoxon signed rank test

Table 1004 Normal or Abnormal (NCS)/Abnormal(CS) cross table for Laboratory Test (Blood Chemistry)

Visit1 (Screening)		Visit14(85d±2d)											
		Medifoam						Betafoam					
		Normal		Abnormal		Total		Normal		Abnormal		Total	
		N	(%)	N	(%)	N	(%)	N	(%)	N	(%)	N	(%)
ALP	Normal	xx	Xx (xx.xx)	xx	xx (xx.xx)	xx	xx (xx.xx)	xx	xx (xx.xx)	xx	xx (xx.xx)	xx	xx (xx.xx)
	Abnormal	xx	Xx (xx.xx)	xx	xx (xx.xx)	xx	xx (xx.xx)	xx	xx (xx.xx)	xx	xx (xx.xx)	xx	xx (xx.xx)
	Total	xx	Xx (xx.xx)	xx	xx (xx.xx)	xx	xx (xx.xx)	xx	xx (xx.xx)	xx	xx (xx.xx)	xx	xx (xx.xx)
P- value		0.xxxx						0.xxxx					
..Rest Variables are omitted in TLF..													

Note1) Normal includes normal and NCS, while abnormal refers to CS.

Note2) p-value: McNemar test

11) Adverse Events  
Analysis Set: Safety

Table 1101 AE Summary (AE, ADE, SAE, SADE)

AE Type	Adverse Event	Treatment	n (Incidence rate)	95% C.I. of Incidence rate	Frequency	Total	P-value
Local	AE	Medifoam	x(x.xx%)	(x.xx,x.xx)	xx	xx	0.xxxx‡
		Betafoam	x(x.xx%)	(x.xx,x.xx)	xx	xx	
		Total	x(x.xx%)	(x.xx,x.xx)	xx	xx	
	ADE	Medifoam	x(x.xx%)	(x.xx,x.xx)	xx	xx	0.xxxx‡
		Betafoam	x(x.xx%)	(x.xx,x.xx)	xx	xx	
		Total	x(x.xx%)	(x.xx,x.xx)	xx	xx	
	SAE	Medifoam	x(x.xx%)	(x.xx,x.xx)	xx	xx	0.xxxx‡
		Betafoam	x(x.xx%)	(x.xx,x.xx)	xx	xx	
		Total	x(x.xx%)	(x.xx,x.xx)	xx	xx	
	SADE	Medifoam	x(x.xx%)	(x.xx,x.xx)	xx	xx	0.xxxx‡
		Betafoam	x(x.xx%)	(x.xx,x.xx)	xx	xx	
		Total	x(x.xx%)	(x.xx,x.xx)	xx	xx	
Other	AE	Medifoam	x(x.xx%)	(x.xx,x.xx)	xx	xx	0.xxxx‡
		Betafoam	x(x.xx%)	(x.xx,x.xx)	xx	xx	
		Total	x(x.xx%)	(x.xx,x.xx)	xx	xx	
	ADE	Medifoam	x(x.xx%)	(x.xx,x.xx)	xx	xx	0.xxxx‡
		Betafoam	x(x.xx%)	(x.xx,x.xx)	xx	xx	
		Total	x(x.xx%)	(x.xx,x.xx)	xx	xx	
	SAE	Medifoam	x(x.xx%)	(x.xx,x.xx)	xx	xx	0.xxxx‡
		Betafoam	x(x.xx%)	(x.xx,x.xx)	xx	xx	
		Total	x(x.xx%)	(x.xx,x.xx)	xx	xx	
	SADE	Medifoam	x(x.xx%)	(x.xx,x.xx)	xx	xx	0.xxxx‡
		Betafoam	x(x.xx%)	(x.xx,x.xx)	xx	xx	
		Total	x(x.xx%)	(x.xx,x.xx)	xx	xx	

Note) ‡: Fisher's exact test

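### The McNemar p-values in the laboratory and physical-examination shift tables (SAP Tables 0801-0813, 1002, 1004) test net change within one arm, so they cannot answer the device-safety question and should be dropped

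*SAP*

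**What the plan says.** SAP section 12 (Dummy Table List) gives the note "Medifoam vs. Betafoam McNemar Test" for Tables 0801-0813 (physical examination), 1002 (hematology) and 1004 (blood chemistry).

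The shells in SAP section 13 are two-by-two cross tables of screening against a later visit, one per arm side by side. Each arm has its own p-value, and there is no between-arm p-value. The footnotes read "Note) p-value: McNemar test" (Tables 0801 and 1002) and "Note2) p-value: McNemar test" (Table 1004). Only clinically significant findings count as abnormal: "Note) Normal includes normal and NCS, while abnormal refers to CS".

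The methods text differs. For laboratory tests, Protocol 15.4 asks the analyst to "tabulate the proportion of normal/abnormal results by time point in each group", and SAP section 8 repeats this: "In addition, tabulate the proportion of normal/abnormal results by time point in each group". Neither names a test. SAP section 8 gives no method for physical examination. Protocol 16.2 states: "This study is a pilot study with no comparator, so that no formal statistical test will be conducted".

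**The concern.** In a randomised two-arm study, a reader of a safety table wants to know how many subjects became abnormal on each device and whether the devices differ. The McNemar null hypothesis is that, within one arm, as many subjects move from normal to CS-abnormal as move back. This is a different question, with three consequences:

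- Nothing in these p-values compares the devices.
- Resolved abnormalities offset new ones in the p-value.
- Any shift over 12 weeks that both arms share counts towards significance.

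A non-significant result may then be taken as reassurance, and a significant one as a device effect. The p-values recur in both arms across 13 physical-examination tables and the tested laboratory parameters. The SAP also does not say whether the exact or the chi-square version applies, and with 10 subjects per arm that choice can decide the result.

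**Working it through.** The plan gives no figure to reproduce here.

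**Inputs.** 10 subjects per arm (Protocol 9). Abnormal means CS only (footnote to Table 0801). Assumed: two-sided 0.05, since no level is stated for this test. Both the exact and the uncorrected chi-square versions are shown. All abnormality rates are assumptions.

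**1. What the test responds to.** Let b be the number newly CS-abnormal and c the number resolved, in one arm. The exact p-value is two-sided from Binomial(b + c, 1/2). The uncorrected statistic is (b − c)²/(b + c) on 1 df.

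- b = 3, c = 3: the statistic is 0/6 = 0, so p = 1.00 in both versions.
- b = 5, c = 0: exact p = 2 × (1/2)⁵ = 0.0625; uncorrected 25/5 = 5, p = 0.025.
- Smallest b reaching 0.05 with c = 0: exact needs 6 (2 × (1/2)⁶ = 0.031); uncorrected needs 4 (16/4 = 4, p = 0.0455).

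**2. It does not compare the arms.** Fisher's exact test on newly abnormal subjects out of 10 per arm serves as the contrast.

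| Arm 1 (new/resolved) | Arm 2 (new/resolved) | Exact McNemar p, arm 1; arm 2 | Fisher p between arms |
|---|---|---|---|
| 6/0 | 6/0 | 0.031; 0.031 | 1.00 |
| 6/0 | 5/0 | 0.031; 0.0625 | 1.00 |
| 5/5 | 0/0 | 1.00; undefined | 0.0325 |

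In the second row one arm looks significant and the other does not, although the arms barely differ. In the third row McNemar shows nothing, although all the new abnormalities are in one arm.

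**3. Change common to both arms.** Suppose nobody is CS-abnormal at screening and both arms have the same true rate r of new abnormality. One arm rejects with probability P = Pr(X ≥ k), where X ~ Binomial(10, r) and k = 4 (uncorrected) or 6 (exact). At least one arm rejects with probability 1 − (1 − P)². At r = 30% uncorrected, P = 0.3504 and 1 − 0.6496² = 0.578.

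| r | Uncorrected, at least one arm | Exact, at least one arm |
|---|---|---|
| 10% | 2.5% | under 0.1% |
| 20% | 23% | 1% |
| 30% | 58% | 9% |
| 40% | 85% | 30% |

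Between-arm Fisher rejects in about 1% of trials at 20% to 40%.

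**4. Table 0801.** It pairs Visit 1 with Visit 2. Protocol 12.1.2 lists the Visit 2 physical examination first and device application later. Protocol 12.1.1 says that when both visits fall on one day, the duplicated examination is done once, so that subject's pair must be concordant. This p-value carries no device information.

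**5. Text against tables.** McNemar appears only in the SAP table list and shells. The laboratory methods text in both documents is descriptive, and SAP section 11 says the analysis in principle follows the protocol's methods.

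**The case against.** A reader might infer that these tables conceal harm. The documents do not support that. Each shell prints all four cells by arm, so the normal-to-abnormal and abnormal-to-normal counts are both visible. Protocol 12.2.3 sends clinically remarkable examination findings after device application to the adverse event section, and Protocol 17.1 counts abnormal laboratory findings as adverse events. Table 1101 compares adverse event incidence between arms with Fisher's exact test, and Tables 1001 and 1003 carry between-arm p-values on the laboratory values. Only the p-value nets off.

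A reader might also take the table-list note as proof that a between-arm test was intended and the wrong one chosen. The device-versus-device label also sits on tables with no test (0304, 0501) and on one-arm tables (0702, 0703), so it may only describe the layout.

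Other points stand in the plan's favour:

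- The rejection rates for identical arms are not errors of McNemar under its own null. If 30% in each arm become abnormal, there is real net change. The fault lies in reading that as a device effect.
- Offsetting needs subjects who are CS-abnormal at screening. No such rate is given, and the exclusions for systemic infection, malnutrition and relevant renal or hepatic disorders may keep it low.
- Low sensitivity is mainly a matter of 10 per arm. With nobody abnormal at screening and new-abnormality rates of 10% against 60%, Fisher rejects in 47% of trials, while McNemar in the worse arm rejects in 63% (exact) or 95% (uncorrected).
- Protocol 16.2 sits in the efficacy chapter, although its sentence speaks of the study as a whole.

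What survives is that these p-values answer no question either document poses, and they invite a reading they cannot bear.

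**Conclusion.** The point holds, with minor severity. The McNemar p-values concern net within-arm change only. They do not compare the devices, can be non-significant beside several new CS abnormalities, and can be significant through change shared by both arms. Table 0801's p-value is uninformative about the device whatever the data show. These conclusions follow from the test and the visit schedule and need no assumed rate.

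The size of any practical error does depend on assumed rates, strongly so: from 2.5% to 58% for identical arms as the common rate goes from 10% to 30% (uncorrected version, nobody abnormal at screening, 10 per arm). It should not be quoted as a property of the trial. No new abnormality is lost from view. This is an exploratory pilot, and neither document attaches a decision rule to these tables.

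**What to change.** Delete the McNemar p-values and footnotes from Tables 0801-0813, 1002 and 1004, remove the test from the Note column of the table list, and drop the Visit 1 against Visit 2 test. Keep the cross tables.

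Add, by arm, for each laboratory parameter and body system, the number of subjects newly CS-abnormal after device application over those not CS-abnormal at screening, with an exact (Clopper-Pearson) 95% interval. Use Visits 3-14 for physical examination and Visit 14 or early completion for laboratory tests. State how many subjects were examined, because SAP 7.2 omits the physical examination at visits outside the site. Give the between-arm difference with a 95% interval, labelled exploratory, and add matching text to SAP section 8.

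The cost is SAP and shell wording and minor reprogramming before analysis; no new data are needed. The intervals will be wide and will look less reassuring than a non-significant p-value: 0 of 10 has an upper limit of 1 − 0.025^(1/10) = 0.308, so a true rate of 31% is not excluded. That is an honest statement of what 10 subjects per arm can show.

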### 13. TLFs

#### 1) Disposition of Subjects

Table 0101 Disposition of Subjects who participated in the study

	Medifoam	Betafoam	Total
Subjects who signed the Informed Consent form	xx(xx.xx%)	xx(xx.xx%)	xx(xx.xx%)
Screening	xx(xx.xx%)	xx(xx.xx%)	xx(xx.xx%)
Screening Failure	xx(xx.xx%)	xx(xx.xx%)	xx(xx.xx%)
Reason for Screening Failure1	xx(xx.xx%)	xx(xx.xx%)	xx(xx.xx%)
Reason for Screening Failure2	xx(xx.xx%)	xx(xx.xx%)	xx(xx.xx%)
Reason for Screening Failure3	xx(xx.xx%)	xx(xx.xx%)	xx(xx.xx%)
Randomized	xx(xx.xx%)	xx(xx.xx%)	xx(xx.xx%)
Reason for Discontinuation 1	xx(xx.xx%)	xx(xx.xx%)	xx(xx.xx%)
Reason for Discontinuation 2	xx(xx.xx%)	xx(xx.xx%)	xx(xx.xx%)
Reason for Discontinuation 3	xx(xx.xx%)	xx(xx.xx%)	xx(xx.xx%)
Subjects who completed the trial (including Early completion)	xx(xx.xx%)	xx(xx.xx%)	xx(xx.xx%)

Table 0102 Detailed reports on discontinued subjects

Treatment Group	Screening No.	Randomization No.	Informed Consent Date	Discontinuation Date	Reason for Discontinuation

Table 0103 Analysis Set

	Medifoam	Betafoam	Total
Randomized	xx(xx.xx%)	xx(xx.xx%)	xx(xx.xx%)
Reason1 for Safety excluded	xx(xx.xx%)	xx(xx.xx%)	xx(xx.xx%)
Reason2 for Safety excluded			
Safety Set	xx(xx.xx%)	xx(xx.xx%)	xx(xx.xx%)
Reason1 for FAS excluded	xx(xx.xx%)	xx(xx.xx%)	xx(xx.xx%)
Reason2 for FAS excluded	xx(xx.xx%)	xx(xx.xx%)	xx(xx.xx%)
FAS	xx(xx.xx%)	xx(xx.xx%)	xx(xx.xx%)

2) Demographics  
Analysis Set: FAS

Table 0201 Demographics

		Medifoam	Betafoam	Total	p-value
Gender	Male	xx(xx.xx%)	xx(xx.xx%)	xx(xx.xx%)	0.xxxx‡
	Female	xx(xx.xx%)	xx(xx.xx%)	xx(xx.xx%)	
	Total	xx(xx.xx%)	xx(xx.xx%)	xx(xx.xx%)	
Age (Years)	N	xx	xx	xx	0.xxxx*
	Mean±Std	xx.xx±x.xx	xx.xx±x.xx	xx.xx±x.xx	
	Median	xx.xx	xx.xx	xx.xx	
	Min~Max	xx.xx~xx.xx	xx.xx~xx.xx	xx.xx~xx.xx	
Age (Categorical)	19~29	xx(xx.xx%)	xx(xx.xx%)	xx(xx.xx%)	0.xxxx‡
	30~39	xx(xx.xx%)	xx(xx.xx%)	xx(xx.xx%)	
	40~49	xx(xx.xx%)	xx(xx.xx%)	xx(xx.xx%)	
	50~59	xx(xx.xx%)	xx(xx.xx%)	xx(xx.xx%)	
	60~69	xx(xx.xx%)	xx(xx.xx%)	xx(xx.xx%)	
	70<	xx(xx.xx%)	xx(xx.xx%)	xx(xx.xx%)	
	Total	xx(xx.xx%)	xx(xx.xx%)	xx(xx.xx%)	
Body Weight (kg)	N	xx	xx	xx	0.xxxx*
	Mean±Std	xx.xx±x.xx	xx.xx±x.xx	xx.xx±x.xx	
	Median	xx.xx	xx.xx	xx.xx	
	Min~Max	xx.xx~xx.xx	xx.xx~xx.xx	xx.xx~xx.xx	
Height (cm)	N	xx	xx	xx	0.xxxx*
	Mean±Std	xx.xx±x.xx	xx.xx±x.xx	xx.xx±x.xx	
	Median	xx.xx	xx.xx	xx.xx	
	Min~Max	xx.xx~xx.xx	xx.xx~xx.xx	xx.xx~xx.xx	
Breast Feeding (Female Only)	Yes	xx(xx.xx%)	xx(xx.xx%)	xx(xx.xx%)	0.xxxx‡
	No	xx(xx.xx%)	xx(xx.xx%)	xx(xx.xx%)	
	Total	xx(xx.xx%)	xx(xx.xx%)	xx(xx.xx%)	
Possibility of Pregnancy (Yes/No)	Yes	xx(xx.xx%)	xx(xx.xx%)	xx(xx.xx%)	0.xxxx‡
	No	xx(xx.xx%)	xx(xx.xx%)	xx(xx.xx%)	
	Total	xx(xx.xx%)	xx(xx.xx%)	xx(xx.xx%)	
Reason for not being able to get pregnant	Menopause 1 year ago	xx(xx.xx%)	xx(xx.xx%)	xx(xx.xx%)	
	Hysterectomy/bilateral ovariectomy surgery	xx(xx.xx%)	xx(xx.xx%)	xx(xx.xx%)	
	Total	xx(xx.xx%)	xx(xx.xx%)	xx(xx.xx%)	
Countermeasure for pregnancy	Yes (Condom)	xx(xx.xx%)	xx(xx.xx%)	xx(xx.xx%)	
	Yes (Oral contraception)	xx(xx.xx%)	xx(xx.xx%)	xx(xx.xx%)	
	Yes (Injectable contraceptive)	xx(xx.xx%)	xx(xx.xx%)	xx(xx.xx%)	

	Yes (Insertable contraceptive)	xx(xx.xx%)	xx(xx.xx%)	xx(xx.xx%)	
	Yes (Intrauterine contraceptive device)	xx(xx.xx%)	xx(xx.xx%)	xx(xx.xx%)	
	Total	xx(xx.xx%)	xx(xx.xx%)	xx(xx.xx%)	
Alcohol consumption	Yes	xx(xx.xx%)	xx(xx.xx%)	xx(xx.xx%)	0.xxxx‡
	No	xx(xx.xx%)	xx(xx.xx%)	xx(xx.xx%)	
	Total	xx(xx.xx%)	xx(xx.xx%)	xx(xx.xx%)	
Alcohol consumption (If yes, alcohol per week)	N	xx	xx	xx	0.xxxx*
	Mean±Std	xx.xx±x.xx	xx.xx±x.xx	xx.xx±x.xx	
	Median	xx.xx	xx.xx	xx.xx	
	Min~Max	xx.xx~xx.xx	xx.xx~xx.xx	xx.xx~xx.xx	
Nicotine consumption	Yes	xx(xx.xx%)	xx(xx.xx%)	xx(xx.xx%)	0.xxxx‡
	No	xx(xx.xx%)	xx(xx.xx%)	xx(xx.xx%)	
	Total	xx(xx.xx%)	xx(xx.xx%)	xx(xx.xx%)	
Nicotine consumption (If yes, cigarettes per day)	N	xx	xx	xx	0.xxxx*
	Mean±Std	xx.xx±x.xx	xx.xx±x.xx	xx.xx±x.xx	
	Median	xx.xx	xx.xx	xx.xx	
	Min~Max	xx.xx~xx.xx	xx.xx~xx.xx	xx.xx~xx.xx	
Urine HCG Test	Done	xx(xx.xx%)	xx(xx.xx%)	xx(xx.xx%)	0.xxxx‡
	Not Done	xx(xx.xx%)	xx(xx.xx%)	xx(xx.xx%)	
	Not Applicable	xx(xx.xx%)	xx(xx.xx%)	xx(xx.xx%)	
	Total	xx(xx.xx%)	xx(xx.xx%)	xx(xx.xx%)	
Urine Test Results	Negative	xx(xx.xx%)	xx(xx.xx%)	xx(xx.xx%)	0.xxxx‡
	Positive	xx(xx.xx%)	xx(xx.xx%)	xx(xx.xx%)	
	Total	xx(xx.xx%)	xx(xx.xx%)	xx(xx.xx%)	

Note) Percentage is based on FAS Set subjects within each column.

Note) \*: t-test, ¥ : Wilcoxon rank sum test, ‡: Fisher's exact test

